1.6 RATIONALE/HYPOTHESIS FOR U2 + VENETOCLAX COMBINATIONS

While venetoclax therapy is highly active in patients with CLL/SLL, relapses occur. Additionally, the majority of patients only achieve a PRs to currently available venetoclax combinations. Further, a practical limitation exists with the TLS risk mitigation strategy required for venetoclax administration, which requires intensive monitoring for patients at medium and high risk of TLS and makes administration challenging in the community setting. We hypothesize that the addition of venetoclax following U2 induction will provide deeper levels of remission than have been achieved with single-agent umbralisib, ublituximab, and venetoclax to date. Further, the sequential strategy has been designed to mitigate the risk of venetoclax related TLS by utilizing a debulking course of U2 prior to initiation of venetoclax. Lastly, sequential monitoring for rate of undetectable MRD will be used to potentially inform future time limited therapies based on the achievement of early optimal response.

Based on the above, we propose this Phase 2/3 trial to evaluate U2 with venetoclax (U2-V) and also to compare the U2 regimen in a randomized fashion to the triplet regimen of U2-V.

The combination of U2-V has been evaluated in an ongoing Phase 1 study (NCT03379051) in patients with relapsed or refractory CLL, which supports the dosing regimen used in this study U2-VEN-207. Of 43 patients treated to date, Grade ≥ 3 AEs were infrequent with neutropenia (21%), leukopenia (12%), and IRRs (7%) occurring in over 5% of patients (Barr et al., 2020). Discontinuations due to AEs were also uncommon with 9% and 4% discontinuing umbralisib and venetoclax respectively. No DLTs were observed during the Phase 1 portion, and the RP2D was found to be umbralisib 800 mg QD, ublituximab 900 mg, and venetoclax at standard dosing. The Phase 1 study utilized a 3 Cycle debulking schedule for U2, similar to this Protocol U2-VEN-207. After 3 cycles of U2 debulking, there was an 81% relative reduction in high- and medium-risk TLS, and no patients developed clinical or laboratory TLS during venetoclax administration. Of 27 patients evaluable at Cycle 12, the triple combination of U2 plus venetoclax produced a 100% ORR, 41% CR, and high rates of uMRD in the peripheral blood (96%) and BM (77%). The findings of the Phase 1 study support continued investigation in the current trial.

U2-VEN-207

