4 STUDY DESIGN

4.1 OVERVIEW OF STUDY DESIGN

This is an open-label, multicenter, Phase 2/3 study designed to investigate the efficacy and safety of U2 combined with venetoclax in subjects with CLL/SLL. Patients with treatment naïve and previously treated CLL/SLL are eligible for enrollment. Based on preliminary results from ongoing ublituximab and umbralisib trials and changing landscape of approved CLL/SLL treatments, single-arm or randomized cohorts may be added for both safety and efficacy.

In the Phase 2 stage of the study (see Figure 8 below), 3 separate cohorts will be enrolled: a cohort of approximately 60 subjects with treatment naïve CLL; a cohort of approximately 60 subjects with previously treated CLL, this includes relapsed subjects who are not refractory to a prior BTK inhibitor; and a cohort of approximately 30 subjects with BTK-refractory CLL will be enrolled in the study. BTK-refractory is defined as disease progression while on, or within 6 months of the last dose of, a BTK inhibitor (e.g. ibrutinib, acalabrutinib, etc.). See Section 8 for details on umbralisib administration based on MRD status. As of January 29, 2021, the Phase 2 portion of the study was closed to enrollment.

FIGURE 8: PHASE 2 STUDY DESIGN

BTK-refractory is defined as disease progression while on, or within 6 months of the last dose of a BTK inhibitor (e.g. ibrutinib, acalabrutinib, etc.)

The Phase 3 stage of the trial (Figure 9) includes 2 independent randomized cohorts of CLL/SLL patients; a treatment naïve cohort and a previously treated cohort. Following screening, qualified patients will be randomized 1:1 to 1 of the 2 arms:

- Arm A: Ublituximab + Umbralisib + Venetoclax (U2-V)
- Arm B: Ublituximab + Umbralisib (U2)

U2-VEN-207

[figure not shown]
Approximately 400 (200 per treatment arm) patients will be enrolled to the treatment naïve CLL/SLL cohort and approximately 300 (150 per treatment arm) patients will be enrolled to the previously treated CLL/SLL cohort. The treatment naïve cohort and the previously treated cohorts will enroll independently of each other.

Patients will be randomized and stratified by the following factors:

Treatment Naïve Cohort: 17p status by central lab (deleted or not deleted) and IGHV status (mutated or not mutated)

Previously Treated Cohort: 17p status by central lab (deleted or not deleted) and BTK status (refractory to BTK; yes or no)

FIGURE 9: PHASE 3 STUDY DESIGN

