12.2.3 Adverse Event/Serious Adverse Event Recording

¹⁷ For females of childbearing potential, serum pregnancy test completed within 3 days prior to Day 1 of Cycle 1.

¹⁸ For females of childbearing potential. This is only required if patients are receiving drug.

²⁰ IgHV to be done at screening if mutation status is not already known.

¹⁹ Baseline BM as clinically indicated as per standard of care. Post-baseline BM biopsy to confirm potential CR required.

²¹ FISH central lab results required for randomization. Samples for FISH, and NGS to be sent to the Central Lab, see lab manual for sample collection and shipment procedures.

²² MRD in peripheral blood at baseline and Cycle 6, Cycle12, Cycle 15 and Cycle 24 (MRD drawn only if subject is in PR or better). One MRD by bone marrow aspirate sample should be completed for all patients MRD negative by peripheral blood. Thereafter, all subjects without signs of clinical progression, repeat MRD every 6 cycles (peripheral blood). Subjects that end treatment prior to Cycle 15 should continue to have MRD collected until month 15. See laboratory manual for collection, processing, and shipment instructions.

²³ A total of 2 serum samples should be collected from each subject for sparse population PK analyses (Pre-dose on Cycle 4, Day 1, and one randomly assigned post-baseline sample). See Section7.2.1 Sparse Sampling **Pharmacokinetics**

²⁴ Samples to be collected pre-dose of ublituximab

²⁵ Response assessment at baseline (within 30 days prior to Cycle 1 Day 1), and within 14 days prior to Cycles 4 & 12, and at least every 6 cycles thereafter. Radiologic assessment should include CT with contrast or MRI imaging of neck, chest, abdomen, and pelvis. BM biopsy to confirm potential CR required. If PD is suspected, scans and relevant clinical data should be sent to central radiology for expedited PD review. This PD confirmation should be obtained prior to subject being removed for PD (except in rare cases where it is in the patients best interest to be discontinued immediately.

²⁶ Venetoclax Cohort Only: TLS risk assessment according to Section 8.5.3.1 at baseline and on Day 1 of Cycle 4, prior to first dose of venetoclax.

27 AEs are to be reported from Cycle 1 Day 1 and SAEs are to be reported from signing of informed consent. A 30-day (± 7 days) and a 90-day (± 7 days) safety follow up visit is required after the last dose of study drug. See Section

Dated: 05 October 2021 (Ver 4.0) U2-VEN-207

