11.3 ANALYSIS POPULATION

The safety population will consist of all subjects who received at least one dose of study drug (ublituximab, umbralisib, or venetoclax). For the Phase 2 component, the ITT population will consist of all subjects who received at least one dose of each study drug (ublituximab, umbralisib, and venetoclax).

U2-VEN-207

For Phase 3, the ITT population will consist of all randomized subjects, regardless of administration of study treatment. Analyses of this population will assign subjects the treatment they were scheduled to receive, regardless of any errors of dosing or dose modifications. Subjects who received treatment in the group that is different from what they have been randomized to, will be noted in the clinical study report. The ITT population is the primary analysis population for efficacy analyses.

The per protocol population will include all ITT subjects without major protocol violations. Major protocol violations will be documented. Analyses based on per protocol population may be performed.

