11.9 SAFETY ANALYSES

Safety analyses will be performed using the safety population. Safety analyses will be primarily based on the incidence, severity, and type of AEs, as well as on clinically meaningful laboratory results, physical examination, and vital signs as available. Safety variables will be tabulated and presented by the dose of ublituximab, umbralisib, and/or venetoclax actually received. Exposure to study treatment and reasons for discontinuation of study treatment will also be tabulated.

Detailed information collected for each AE will be included in a listing: AE term, start/stop dates of the AE, seriousness, severity, relationship to study drug(s), action taken, and outcome. In addition, the number and percentage of subjects experiencing at least one treatment-emergent AE will be tabulated by body system, preferred term, and CTCAE grade. Treatment-emergent AEs, drug-related AEs, AESIs, SAEs, AEs with a fatal outcome, and AEs leading to discontinuation/dose modification will be further summarized. Summary statistics for actual values and for changes from baseline will be tabulated for clinical laboratory results by scheduled visit. Subjects with laboratory values outside of the normal reference range at any post-baseline assessment will be summarized and graded per NCI CTCAE Version 5.0 as applicable. Subject incidence of abnormal laboratory results will be summarized by treatment group and maximum grade for each abnormal laboratory finding.

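### Section 11.9 groups safety by dose actually received; read as drugs received, Arm A subjects who never start venetoclax would be tabulated with U2

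*Combined protocol and SAP*

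**What the plan says.** The presentation rule for safety is in Section 11.9: "Safety variables will be tabulated and presented by the dose of ublituximab, umbralisib, and/or venetoclax actually received". Later in the section a different term appears: "Subject incidence of abnormal laboratory results will be summarized by treatment group and maximum grade for each abnormal laboratory finding". Treatment group is not defined there or in Section 11.3.

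Section 11.3 puts anyone with at least one dose of any of the three drugs in the safety population. That settles who is counted, not the column in which they are shown. The only as-assigned rule in Section 11.3 is written for the Phase 3 ITT population: "Analyses of this population will assign subjects the treatment they were scheduled to receive, regardless of any errors of dosing or dose modifications".

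Venetoclax starts late by design. Section 1.6 describes "utilizing a debulking course of U2 prior to initiation of venetoclax", and footnote 26 to Table 5 (Section 6) places the second tumour lysis risk assessment "on Day 1 of Cycle 4, prior to first dose of venetoclax". Tables 10 and 11 (Sections 8.3 and 8.4) give the two arms the same ublituximab and umbralisib in Cycles 1-3.

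**The concern.** Grouping by treatment received is usually harmless, because it moves only the few subjects dosed in error. Here the experimental regimen begins with a lead-in identical to the control regimen. An Arm A subject who stops during Cycles 1-3 has received exactly U2 without any error.

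If columns follow the drugs taken, entry to the U2-V column depends on something that happens after randomisation and that toxicity itself affects. Subjects whose early toxicity kept them from venetoclax would leave the U2-V numerator and denominator and join those of U2. Randomisation would no longer protect the comparison. Section 11.11.3 says the interim analysis assesses safety of U2-V against U2, so these tables bear on the DSMB's advice as well as the final report.

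The undefined laboratory grouping adds a separate problem: adverse event and laboratory tables could have different denominators under similar column labels.

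**Working it through.** **Plan's own figure.** There is none to reproduce. The documents attach no number to this grouping rule.

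**Inputs from the documents**
- Arm sizes (Section 4.1): for the treatment naïve cohort, "Approximately 400 (200 per treatment arm) patients will be enrolled"; for the previously treated cohort, about 150 per arm.
- Lead-in before venetoclax: 3 cycles × 28 days = 84 days, or 12 weeks.
- Early-stopping rate: not given. Section 1.6 reports that, of 43 Phase 1 patients on the triplet, 9% stopped umbralisib and 4% stopped venetoclax for adverse events, without timing.

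**Assumptions.** All randomised subjects are treated. The true event rate p is equal in the two arms, at 20%, 30% or 40%. The share of Arm A that never starts venetoclax is 2%, 5% or 10%.

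**Formulas.** Let n be the arm size, x = np the events per arm, m the Arm A subjects who never start venetoclax, and q the event rate among those m.
- By randomised arm: x/n in each arm, difference 0.
- By drugs received: U2-V = (x − mq)/(n − m); U2 = (x + mq)/(n + m).

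**Treatment naïve cohort, p = 30%, 5% early stopping.** n = 200, x = 60, m = 10.
- Worst case, q = 1: U2-V = 50/190 = 26.3%; U2 = 70/210 = 33.3%; difference −7.0 points.
- Early stoppers no different from the rest, q = 0.3: U2-V = 57/190 = 30.0%; U2 = 63/210 = 30.0%; difference 0.

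The false difference therefore comes from early stoppers having the event more often than others. That is expected for events that cause stopping. For late-onset events, which early stoppers have little time to develop, q can fall below p and the sign can reverse.

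**Range for 200 per arm, worst case (q = 1), U2-V minus U2 in percentage points**

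| Never start venetoclax | Moved | p = 20% | p = 30% | p = 40% |
|---|---|---|---|---|
| 2% | 4 | −3.2 | −2.8 | −2.4 |
| 5% | 10 | −8.0 | −7.0 | −6.0 |
| 10% | 20 | −16.2 | −14.1 | −12.1 |

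**Previously treated cohort, p = 30%, 5% early stopping.** n = 150, x = 45, and 7.5 is rounded up to m = 8. U2-V = 37/142 = 26.1%; U2 = 53/158 = 33.5%; difference −7.5 points.

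**Adverse events that end all treatment before Cycle 4.** Here q = 1 by definition. With a true 10/200 = 5% in each treatment naïve arm, the tables would show 0/190 = 0% for U2-V and (10 + 10)/210 = 9.5% for U2.

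**The case against.** The strongest reply is that the documents never say that Arm A early stoppers are counted as U2. A reader might infer that from Section 11.9, but the text speaks of dose received, not regimen or arm received, and could mean a display by dose level. The phrase treatment group in the same section may name the columns intended throughout. Section 11.3 describes a departure as being treated in a group other than the randomised one, and an Arm A subject who stops in Cycle 2 has received what Arm A prescribes up to then. Section 11 defers detail to a Statistical Analysis Plan, and no separate SAP text is in the material reviewed, so a column rule there cannot be excluded. All this stands against calling the reclassification a stated rule.

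It does not clear the wording. A display by dose level also groups subjects on a post-randomisation quantity that toxicity affects. A SAP that follows the sentence literally would carry the problem forward. Section 11.3 already makes reaching venetoclax a condition elsewhere: the Phase 2 ITT population requires a dose of each drug.

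Two further inferences go too far. One is that infusion reactions and other early events in general would leave the U2-V column. Only subjects who never start venetoclax could move; early events in those who go on to Cycle 4 stay in U2-V. The other is that the documents imply a particular size of bias. They give no early-stopping rate, and pooling 350 per arm would merge cohorts that the plan evaluates independently. Section 8.5.4 lets a subject stop one drug and continue the others, so stopping umbralisib early need not prevent venetoclax, while a subject who never starts venetoclax may stay on U2.

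Some outputs also lie outside this grouping: the OS analysis uses the ITT population (Section 11.11.2.6), and the discontinuation stopping rules count enrolled patients (Section 11.11.5).

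**Conclusion.** The concern holds in conditional form. Section 11.9 gives a grouping rule based on what was received, leaves treatment group undefined, and no rule keeps Arm A subjects in Arm A for safety. With a 12-week lead-in identical to the control regimen, reading the rule as drugs received would make the U2-V column conditional on reaching venetoclax and would bias the Phase 3 comparison in favour of U2-V for events linked to early stopping.

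The size is unknown. The 26.3% against 33.3% illustration rests on assumed rates and on every early stopper having the event; it is an upper case for those inputs, not a forecast. The plan should be corrected because the sentence as written permits this grouping, not because it is known that it will be applied. Phase 3 efficacy, analysed by ITT, is unaffected.

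**What to change.** Limit the as-received sentence in Section 11.9 so that it no longer governs Phase 3, and add, with the same text in the SAP:

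*For Phase 3, all safety summaries will be presented separately for each cohort, by randomised arm among subjects given at least one dose of any study drug. Arm A subjects who stop before venetoclax remain in Arm A. A subject is tabulated under the other arm only if that arm's regimen was given in error. Treatment group has this meaning throughout the section. As a supportive analysis, adverse events will also be summarised for Cycles 1-3 and from Cycle 4 onward. Phase 2 safety will be summarised by cohort.*

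The last sentence is needed because Section 11.9 also covers Phase 2, which has no randomised arms; it agrees with the by-cohort convention in Section 11.2. The supportive split shows toxicity after venetoclax is added without letting it define the main columns.

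The cost is a short paragraph and one additional set of tables. Randomised arm, dosing dates and event dates are already collected, so no new data are needed.

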6 STUDY ASSESSMENT AND TREATMENT SCHEDULE (PHASE

The table below lists all of the required assessments that should be performed at each study visit for subjects enrolled to the Phase 3 stage of the trial (version 3.0+).

TABLE 5: STUDY ASSESSMENT AND TREATMENT SCHEDULE

							_										
EOS,8				×			X			X	X	×					
LTFU7																	
30-and 90-Day Safety FU ⁶																	
ЕОТ				×			X			X	X	X					
Cycle 18 and Q3 Cycle ⁵	D1			X			X		X	X	X	×					X
Cycles 9, 12, 15 ⁵	D1			×			X		X	X	X	×					X
Cycles 5&6³	D1			X			Х		X	X	X	X					X
	D22									X		×					
Cycle 4 ⁴	D15									X		×					
Cyc	D8									X		X12					
	D1			X			X		X	X	X	X11					X
Cycles 2-3³	D1			X			X		X	X	X	×					
	D15									X	X	X					
Cycle 1 ²	D8									X	X	×					
Cy	D2									X	X	X					
	D1			×			X		X	X	X	×					
Screening ¹	D-30 to D0	X	X	X			X		X	X	X	X			X	X	X
Cycle = 28 days	Procedure/Days	Medical history	Rai Staging	ECOG	Performance	Status	Physical	Examination	Weight	Vital signs ⁹	Hematology ¹⁰	Chemistry, LDH,	Mg, Phos, Uric	acid10	PT/INR13	Hep B/C14	CMV15

Screening labs (hematology and chemistry only) must be conducted within 14 days prior to Cycle 1 Day 1. Patients must continue to meet eligibility criteria in respect to adequate organ system function as per Inclusion Criteria # 2 within the required screening timeframe, and importantly, on Cycle 1 Day 1. Hematology and chemistry results must be reviewed prior to dosing on Cycle 1 Day 1 to ensure subjects meet Inclusion #2 as per

² Study visits have a ±1 day window.

³ Study visits have a ±3 day window.

[·] Cycle 4 Day 8, 15, and 22 visits only for subject randomized to Arm A (U2-V). Study visits have a±3 day window.

⁵ Study visits have a ± 7 day window.

^{&#}x27;Subjects who discontinue from study treatment (for reasons other than progressive disease) will continue to be followed for progression until a non-protocol line of therapy is initiated. LTFU for PD and OS should be s A 30-day (± 7 days) and a 90-day (± 7 days) safety follow up visit is required after the last dose of study drug. See Section 12.2.3 Adverse Event/Serious Adverse Event Recording. entered approximately every 6 months. Enter date of disease progression and/or death occurred in eCRF.

Bind of Study (EOS) visit to be completed for subjects who are coming off study. Tumor Assessment should be performed if not done within previous 3 months. EOT and EOS may be the same visit if subject is discontinuing

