the study drugs and is not going into LTFU. 9 Heart rate, blood pressure, temperature, respirations.

¹⁰ Hematology and chemistry must be done prior to ublitaximab administration.

¹¹ See Section 8.5.3: Guidelines for Administration of Venetoclax for dose ramp-up schedule and recommended blood chemistry monitoring based on tumor burden.

¹² Cycle 4, day 8, 15 and 22 only required for patients receiving venetoclax and during the venetoclax ramp-up.
13 PT/INR to be done at screening and as clinically indicated. INR should be monitored closely in subjects receiving venetoclax and warfarin.

¹⁴ Serum virology to include HBsAg, HBcAb and HCV AB. If HBcAb is positive subjects must be evaluated for the presence of active HBV by PCR. If HCV AB positive, subjects must be evaluated for the presence of HCV by

¹⁵ At baseline, CMV IgG and IgM or CMV by PCR (if institutions SOC). Thereafter, CMV by PCR for all subjects while receiving umbralisib beginning C4D1, then C6D1 and approximately every 3 cycles thereafter up to Cycle

^{24,} then approximately every 6 cycles thereafter. If CMV IgM or IgG is positive, subjects must be evaluated for the presence of active CMV by PCR U2-VEN-207

	_		_			_		_	_	_		_	_				
E0S,8														X			X
LTFU7											X			X			
30-and 90-Day Safety FU ⁶																×	
EOT																×	×
Cycle 18 and Q3 Cycle ⁵	D1	C24									C24			X25		X	X
Cycles 9, 12, 15s	D1	C12			X						C12 and C15		C12	X25		X	X
Cycles 5&6 ³	D1				X						90		90			×	X
	D22															×	
Cycle 44	D15															×	
Cyc	8Q															×	
	D1				X							X		X	×	×	X
Cycles 2-33	D1				X								E)			X	X
	D15												X			×	X
Cycle 1 ²	8Q															×	X
Č	D2															×	X
	D1												X			×	X
Screening ¹	D-30 to D0	X	X	X		X19		X	X^{20}	X	X			X	X	×	
Cycle = 28 days	Procedure/Days	Quant IgG, IgA, IgM16	β ₂ -microglobulin	Serum Pregnancy Test ¹⁷	Urine Pregnancy ¹⁸	BM	biopsy/aspirate	EKG	AH9I	FISH and NGS ²¹	MRD ²²	Sparse PK ²³	Immunogenicity ²⁴	Response Assessment ²⁵	TLS Risk- Assessment ²⁶	AE Assessment ²⁷	Con Med Assessment

¹⁶ To be completed at baseline, during Cycle 12, and during Cycle 24 only.

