8.5.3.1 TUMOR LYSIS SYNDROME

U2-VEN-207

Venetoclax can cause rapid reduction in tumor and thus poses a risk for tumor lysis syndrome (TLS) in the initial 5-week ramp-up phase. Changes in blood chemistries consistent with TLS that require prompt management can occur as early as 6 to 8 hours following the first dose of venetoclax and at each dose increase. The risk of TLS is a continuum based on multiple factors, including tumor burden and comorbidities. Perform tumor burden assessments, including radiographic evaluation (e.g., CT scan), assess blood chemistry (potassium, uric acid, phosphorus, calcium, and creatinine) in all subjects and correct pre-existing abnormalities prior to initiation of treatment with venetoclax. Reduced renal function (creatinine clearance <80 mL/min) further increases the risk. The risk may decrease as tumor burden decreases (https://www.accessdata.fda.gov/drugsatfda_docs/label/2018/208573s009lbl.pdf). See venetoclax full prescribing information.

TABLE 19: REQUIRED TLS PROPHYLAXIS BASED ON TUMOR BURDEN FROM VENETOCLAX PACKAGE INSERT

Tumor Burden		Prophylaxis		Blood Chemistry Monitoring
Tulliof Burdell		Hydration ^a	Anti- hyperuricemics	Setting and Frequency of Assessments ^{c, d}
Low	All LN <5 cm AND ALC <25 x10 ⁹ /L	Oral (1.5-2 L)	Allopurinol ^b	 Outpatient For first dose of 20 mg and 50 mg: Pre-dose, 6 to 8 hours, 24 hours For subsequent ramp-up doses: Pre-dose
Medium	Any LN 5 cm to <10 cm OR ALC ≥25 x10 ⁹ /L	Oral (1.5-2 L) and consider additional intravenous	Allopurinol	Outpatient • For first dose of 20 mg and 50 mg: Pre-dose, 6 to 8 hours, 24 hours • For subsequent ramp-up doses: Pre-dose • For first dose of 20 mg and 50 mg: Consider hospitalization for patients with CrCl <80 mL/min; see below for monitoring in hospital
High	Any LN ≥10 cm OR ALC ≥25 x 10°/L AND Any LN ≥5 cm	Oral (1.5-2L) and intravenous (150-200 mL/hr as tolerated)	Allopurinol; consider rasburicase if baseline uric acid is elevated	In hospital • For first dose of 20 mg and 50 mg: Pre-dose, 4, 8, 12 and 24 hours Outpatient • For subsequent ramp-up doses: Pre-dose, 6 to 8 hours, 24 hours

ALC = absolute lymphocyte count; LN = lymph node.

U2-VEN-207

^a Administer intravenous hydration for any subject who cannot tolerate oral hydration.

^b Start allopurinol or xanthine oxidase inhibitor 2 to 3 days prior to initiation of venetoclax.

- ^c Evaluate blood chemistries (potassium, uric acid, phosphorus, calcium, and creatinine); review in real time.

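### Chemistry is sampled more often in Arm A during venetoclax ramp-up, so the by-arm any-value and worst-grade chemistry tables in Section 11.9 mix drug effect with sampling intensity

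*Combined protocol and SAP*

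**What the plan says.** Section 11.9 sets two incidence rules for laboratory data. The first is "Subjects with laboratory values outside of the normal reference range at any post-baseline assessment will be summarized", with CTCAE grading. The second is "Subject incidence of abnormal laboratory results will be summarized by treatment group and maximum grade for each abnormal laboratory finding". Neither carries a time window, a restriction to common visits or an adjustment for the number of draws. The section also promises a matched-visit display: "Summary statistics for actual values and for changes from baseline will be tabulated for clinical laboratory results by scheduled visit".

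The Phase 3 schedule in Section 6 (Table 5) treats the arms differently in Cycle 4. The Day 8, 15 and 22 visits belong to Arm A alone, and the chemistry footnote reads "Cycle 4, day 8, 15 and 22 only required for patients receiving venetoclax and during the venetoclax ramp-up". Section 8.5.3.1 adds timed chemistry over the "initial 5-week ramp-up phase". For low and medium TLS risk, Table 19 asks: "For first dose of 20 mg and 50 mg: Pre-dose, 6 to 8 hours, 24 hours". High-risk subjects have five draws at each of those two doses and three at each later step. Footnote d adds post-dose draws at later steps for subjects at risk. The timed draws cover potassium, uric acid, phosphorus, calcium and creatinine.

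Section 11 defers further detail to a Statistical Analysis Plan. Nothing in the text available narrows the rules above.

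**The concern.** The share of subjects with at least one abnormal value, and the distribution of worst grade, both rise with the number of samples taken, even when the underlying risk is the same. If one arm is sampled more often by design, a by-arm table of these quantities cannot separate a drug effect from more intensive looking.

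The table matters because Section 12.2.3.1 keeps most isolated laboratory abnormalities out of adverse event reporting unless stated conditions are met. The Section 11.9 summaries are therefore a main place where U2-V and U2 will be compared on these analytes. The imbalance starts while both arms are on treatment, so it is not just another form of the difference in treatment duration.

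**Working it through.** The plan states no draw count or ratio, so there is no figure to reproduce. The counts below come from Table 5 and from Table 19 with footnote d.

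**Step 1: draws around ramp-up.** The venetoclax steps are 20, 50, 100 and 200 mg in Cycle 4 and 400 mg from Cycle 5 Day 1. Arm B has chemistry on Cycle 4 Day 1 and Cycle 5 Day 1, which is 2 draws. Arm A draws at the five steps:

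- Table 5 visits only: 1+1+1+1+1 = 5, ratio 5/2 = 2.5
- Low or medium TLS risk, Table 19 body: 3+3+1+1+1 = 9, ratio 4.5
- The same with footnote d at later steps: 3+3+3+3+3 = 15, ratio 7.5
- High TLS risk: 5+5+3+3+3 = 19, ratio 9.5

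Cycle 4 alone, without the Cycle 5 Day 1 dose, gives 4, 8, 12 or 16 versus 1. The Table 19 body and footnote d can be read as giving different schedules for low- and medium-risk subjects. I carry both counts and do not choose between them.

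**Step 2: draws over the window that Section 11.9 uses.** The rule is any post-baseline value, so the four-week count is not the one that describes the table. Taking Cycle 1 Day 1 as baseline, the visits scheduled in both arms to Cycle 15 are Cycle 1 Days 2, 8 and 15 (3), Day 1 of Cycles 2 to 6 (5), and Day 1 of Cycles 9, 12 and 15 (3): 11 in all. Arm A adds its step 1 count minus the 2 shared draws, which is 3, 7, 13 or 17.

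**Step 3: effect with no true difference.** P(at least one abnormal) = 1 − (1 − p)^n, with independent draws and the same p in both arms. The documents give no p; 2% is an assumption. For Arm B, 1 − 0.98^11 = 19.9%.

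| Arm A monitoring | Draws to Cycle 15 (Arm B 11) | Ratio | P at p = 2% (Arm B 19.9%) |
|---|---|---|---|
| Table 5 visits only | 14 | 1.27 | 24.6% |
| Low/medium risk | 18 | 1.64 | 30.5% |
| Low/medium with footnote d | 24 | 2.18 | 38.4% |
| High risk | 28 | 2.55 | 43.2% |

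Across other values of p, Arm B versus the Arm A range is 5.4% versus 6.8% to 13.1% at p = 0.5%, 10.5% versus 13.1% to 24.5% at 1%, and 43.1% versus 51.2% to 76.2% at 5%.

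**Step 4: after Cycle 15.** The Arm A regimen ends at Cycle 15. Arm B continues, with chemistry every 3 cycles from Cycle 18. An Arm B subject still on treatment reaches the Arm A count after 3, 7, 13 or 17 further draws, at Cycle 15 + 3 × (extra draws) = 24, 36, 54 or 66. With 28-day cycles that is about 22, 33, 50 or 61 months.

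**Step 5: which tests are affected.** Table 5 shows chemistry but no hematology on Cycle 4 Days 8, 15 and 22, and the timed draws are chemistry only.

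**The case against.** A reader might infer that any U2-V excess in the laboratory table will be an artefact of sampling. The documents do not support that. Section 8.5.3.1 describes a real venetoclax effect on these analytes, so true effect and detection are mixed, and the size of the detection part depends on a per-draw rate that is not given.

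A reader might also apply the ratio of 2.5 to 9.5 to the Section 11.9 table, or take the direction as fixed. Neither holds. The ratio belongs to the short window in step 1; the table is cumulative, with 1.27 to 2.55 to Cycle 15, and Arm B's continuing visits work the other way. The upper end also needs high TLS risk at Cycle 4. Section 1.6 reports an 81% relative reduction in high- and medium-risk TLS after the similar three-cycle debulking schedule in the Phase 1 study, so few subjects may be there.

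Extending the point to adverse event counts is weak, because Section 12.2.3 records these from Cycle 1 Day 1 to 30 days after treatment, whatever the number of visits.

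It is also fair to say that the laboratory summary is descriptive, that Section 11.9 has a by-visit table, and that a separate analysis plan might narrow the window or leave out the timed draws. The by-visit table, however, gives values and changes, not incidence or worst grade. Section 7.1 lists the post-dose ramp-up tests among the protocol's laboratory assessments, and the three extra visits are in Table 5 in any case. The later offset from Arm B does not repair the comparison: two distortions of different timing do not cancel reliably. The DSMB reviews safety about every 6 to 9 months (Section 13.1), and a subject in Arm B reaches the Arm A count at about 22 months at the earliest.

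The strongest part of the opposing case concerns the remedy. Replacing the main table with common visits would remove the post-dose values where ramp-up toxicity would appear, along with late and unscheduled worst grades. That stands, and it is why the existing table should be kept.

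**Conclusion.** The point holds in a limited form. As written, the by-arm incidence and worst-grade summaries for potassium, phosphorus, calcium, uric acid and creatinine confound drug effect with sampling intensity and can inflate a U2-V excess that arises in ramp-up. To Cycle 15 the scheduled imbalance is 11 draws versus 14 to 28. Under equal risk and an independent 2% per draw, that alone gives 19.9% versus 24.6% to 43.2%. These percentages illustrate the mechanism and do not predict the result: p is assumed, and draws taken hours apart in one subject are correlated, so the true inflation is smaller. With longer follow-up the imbalance can shrink or reverse. The efficacy analyses and hematology are not touched. This is an inexpensive improvement to the safety reporting.

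**What to change.** Three changes to Section 11.9 or the analysis plan:

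1. Keep the summary of maximum grade over all post-baseline values, with a note that chemistry sampling was unequal by arm during ramp-up and after Cycle 15.
2. Add a by-arm incidence and maximum-grade table for chemistry limited to visits scheduled in both arms: the post-baseline Cycle 1 visits and Day 1 of Cycles 2 to 6, 9, 12 and 15. On Cycle 4 Day 1 and Cycle 5 Day 1, use the pre-dose draw. Each arm then has 11 scheduled draws.
3. Put the Cycle 4 Day 8, 15 and 22 draws and the post-dose ramp-up draws in a separate Arm A TLS-monitoring table.

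The cost is some wording and one or two extra tables, with no change to visits, sampling or treatment. The common-visit table must not be read alone, because it leaves out post-dose TLS changes; its footnote should say so and point to the other two tables.
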